11.2 Secondary Efficacy Endpoint(s)

The secondary efficacy endpoints are:

Annualized bleeding rate (ABR) (counts/yr.)

 $= \frac{\text{Number of bleeding episodes during calculation period}}{\text{Total number of days during the calculation period}} \times 365.25$

Annualized FVIII use (IU/kg/yr.)

 $= \frac{\text{Sum of FVIII use(IU/kg) during calculation period}}{\text{Total number of days during the calculation period}} \times 365.25$

Annualized FVIII infusion rate (count/yr.)

Proprietary and Confidential Pg. 17 of 38

= Number of FVIII replacement infusions during calculation period

Total number of days during the calculation period

Subjects will be asked at each study visit to report the number of bleeding episodes and the use of factor replacement therapy since the previous visit. This information will be captured on the subject's diary or other subject records. A bleeding episode is defined as a bleed or symptoms associated with the development of a bleed (or multiple bleeds occurred in the same day) requiring FVIII replacement treatment.

The calculation period in the above formulas for post-baseline values will be Weeks 1-4, Weeks 5-26, Weeks 5-52, and Weeks 5 and beyond.

The baseline values for the secondary endpoints will be based on the historical data prior to study enrollment.

The ABR by individual subject and ABR descriptive statistics over time (pre-infusion and post-infusion calculation periods) by cohort will be tabulated. Such tabulation may also be performed for subgroups defined by baseline FVIII treatment regimen (on-demand vs. prophylaxis). The same tabulation will be performed for ABR before FVIII activity achieving 5 IU/dL and ABR after FVIII activity achieving 5 IU/dL. The ABR change from pre-infusion will be summarized by cohort. Summaries by the bleeding site (target joint, non-target joint), bleeding cause (spontaneous, traumatic), by cohort may also be performed for ABR. Scatter plots of post-infusion individual bleeding episodes over time will be plotted. A comparison of pre-infusion and post-infusion ABR using Poisson regression model followed by a test for overdispersion will be performed. The ABR will be analyzed using negative binomial regression if overdispersion exists. A comparison using a Wilcoxon signed-rank test may also be performed.

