The above ABR analyses will be repeated for treated bleeds, as defined using standard criteria defined by the Subcommittee on Standards and Criteria, FVIII/FIX subcommittee of the International Society of Thrombosis and Hemostasis. A bleed is considered to be a "treated bleed" if it is directly followed by a haemophilia medication reported to be a "treatment for bleeding episode" irrespective of the time between the treatment and the preceding bleed (i.e., there is not an intervening bleed). A bleed and the first treatment thereafter are considered to be pairs (i.e., one treatment belongs to one bleed only), with the following exception: if multiple bleeds occur on the same calendar day, the subsequent treatment is considered to apply for each of these multiple bleeds (which are, however, counted as separate treated bleeds). Bleeds due to surgery/procedure are not included in the primary analysis. Only treatments that were recorded as "treatment for bleeding episode" are included in the determination of a treated bleed. Two bleeds at the same anatomical location are considered to be one bleed if the second occurs within 72 hours from the last treatment for the first bleed. The last treatment is defined as the last treatment before a new bleed occurs, either in the same or in a different location. This is in line with the above definition that bleeds and treatments are considered to be pairs.

The Annualized FVIII use and Annualized FVIII infusion rate will be analyzed similarly as ABR. The post-infusion and pre-infusion annualized FVIII use will be compared using a paired t-test. The FVIII replacement treatment by the following different categories will also be summarized:

- Treatment for adverse events (including all bleeds, and symptoms associated with the development of a bleed or bruises that would occur in a non-haemophiliac person per protocol)
- Treatment for bleeding episode (including all bleeds, and symptoms associated with the
 development of a bleed or bruises that are normal events of haemophilia but should not be
 treated as AEs per protocol)
- Prophylaxis (routine)
- Surgery/procedure
- Prophylaxis (precautionary due to activity/injury)

The analyses described for the secondary endpoints will be conducted for the FAS analysis population. Sensitivity analyses using PP analysis population may be performed for secondary endpoints, if applicable.

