12.1 Adverse Events

Only treatment-emergent adverse events (TEAEs) occurring and reported during the study period will be included in the adverse event summaries. A TEAE is defined as any AE that newly appeared, increased in frequency, or worsened in severity following initiation of study drug administration. Adverse events will be coded in accordance with Medical Dictionary for Regulatory Activities (MedDRA).

An adverse drug reaction (ADR) is any AE for which there is a reasonable possibility that the study drug caused the AE. The investigator will assess the causality for individual AEs, applying the guidance specified in protocol, and those assessed as study drug-related will be considered ADRs.

A serious adverse event (SAE) is any untoward medical occurrence that at any dose meets one or more of the seriousness criteria enumerated in the protocol. AE severity, not equivalent to seriousness, will be assessed using the protocol defined categories using the NCI CTCAE v4.03.

All bleeding events and suspected bleeding events, regardless of the need for exogenous FVIII therapy as treatment, should be captured in subject diaries and recorded on the designated bleeding eCRF. Bleeding

Proprietary and Confidential Pg. 20 of 38

events and suspected bleeding events should not be reported as adverse events, with the following exception:

 All bleeding events and suspected bleeding events which meet one or more of the criteria for being serious (refer to protocol Section 10.2) should be reported as serious adverse events (whether or not they are bleeding events that are normal sequelae of haemophilia, and whether or not they required exogenous FVIII as treatment).

The study AE reporting period is as follows: After informed consent but prior to initiation of study treatment, only SAEs associated with any protocol-imposed interventions will be reported. After informed consent is obtained and the administration of study drug, the reporting period for all non-serious AEs and SAEs begins and continues for approximately 5 years or until study discontinuation/termination, whichever is later.

The following types of AEs will be summarized: all AEs, AEs assessed by investigator as related, SAEs, SAEs assessed by investigator as related, AEs leading to study discontinuation, deaths, EOSIs. Listings will be provided.

If the onset date or end date of an AE is partial, the same imputation rules described in Section 3.5will be applied.

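### The treated-bleed ABR depends on a treatment category that SAP Sections 11.2 and 12.1 define inconsistently, so a bleed treated with FVIII can be left out of the count

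*SAP*

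**What the plan says.** Section 11.2 of the SAP contains two bleed counts. The first underlies the ABR endpoint. A bleeding episode is a bleed, or symptoms of a developing bleed ("or multiple bleeds occurred in the same day) requiring FVIII replacement treatment"). It has no filter on how the infusion was categorised.

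The second is an added analysis: "The above ABR analyses will be repeated for treated bleeds". Here a bleed must be followed by a medication in the bleeding-episode category, "irrespective of the time between the treatment and the preceding bleed (i.e., there is not an intervening bleed"). The restriction is explicit: "Only treatments that were recorded as 'treatment for bleeding episode' are included in the determination of a treated bleed".

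The section then lists the categories of FVIII replacement to be summarised. One is "Treatment for adverse events (including all bleeds, and symptoms associated with the development of a bleed or bruises that would occur in a non-haemophiliac person"). The next, for bleeding episodes, covers bleeds that are normal for haemophilia and are not to be handled as adverse events. Both descriptions defer to the protocol.

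Section 12.1 says that all bleeds go on the bleeding eCRF and that bleeding events and "suspected bleeding events should not be reported as adverse events", with one exception. Bleeds meeting a seriousness criterion "should be reported as serious adverse events (whether or not they are bleeding events that are normal sequelae of haemophilia", and whether or not FVIII was needed.

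**The concern.** Section 11.2 expects FVIII for some bleeds to be recorded outside the only category that can make a bleed treated. It neither acknowledges nor justifies the resulting exclusion. The boundary between the two categories is also unstable: Section 11.2 draws it by whether a person without haemophilia would have had the bleed, and Section 12.1 by seriousness.

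Two sites could therefore categorise the same infusion differently, each following a part of the SAP, and the treated-bleed count would differ. The treated-bleed version carries the full set of ABR analyses, including the pre/post comparison. Treated bleeds and treated joint bleeds are also the outcomes in the Section 11.2.1 regression on FVIII activity. With at most 15 subjects dosed (Section 2.5), a single bleed can move a cohort summary.

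**Working it through.** The SAP states no figure on this point, so the check is mainly one of text.

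**Step 1. Sort each kind of FVIII-treated bleed under both sections.**

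| Bleed | Section 11.2 category | Section 12.1 status | Does its FVIII qualify? |
|---|---|---|---|
| Non-serious, normal for haemophilia | Bleeding episode | Not an AE | Yes |
| Non-serious, would also occur without haemophilia | Adverse event | Not an AE | No under 11.2; the sections conflict |
| Serious, normal for haemophilia | Bleeding episode by type, but that category is for bleeds not handled as AEs | SAE | Unclear |
| Serious, would also occur without haemophilia | Adverse event | SAE | No; the sections agree |

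Only the first row is clean. In the second the sections disagree, in the third the category cannot be determined, and in the fourth both sections point to the adverse-event category, so a serious bleed treated with FVIII does not qualify through that infusion.

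**Step 2. Is omission automatic?** No. The pairing rule has no time limit. A bleed whose own FVIII was put in the adverse-event category still counts if a later bleeding-episode infusion follows with no other bleed in between. If another bleed comes first, or no such infusion follows, the bleed is omitted.

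**Step 3. Effect per omitted bleed.** Inputs: the ABR formula in Section 11.2 (count / days × 365.25) and the windows in Appendix 17.1.

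- Weeks 5-26, Days 33 to 186: 186 − 33 + 1 = 154 days; 365.25 / 154 = 2.37 per year.
- Weeks 5-52, Days 33 to 368: 368 − 33 + 1 = 336 days; 365.25 / 336 = 1.09 per year.
- Weeks 5 and beyond, assuming follow-up to the end of the Week 260 FVIII-activity window (Day 1841): 1841 − 33 + 1 = 1809 days; 365.25 / 1809 = 0.20 per year. Shorter follow-up gives a larger effect.

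**Step 4. Illustration.** Assume one subject with 3 FVIII-treated bleeds on separate days in Weeks 5-52. The main ABR is 3 × 365.25 / 336 = 3.26 per year however the infusions are categorised. The treated-bleed ABR depends on how many of the three are in the adverse-event category and unpaired:

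| In AE category, unpaired | Treated-bleed ABR (per year) |
|---|---|
| 0 | 3.26 |
| 1 | 2.17 |
| 2 | 1.09 |
| 3 | 0 |

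The SAP gives no basis for choosing among these rows, and the first may be the true one.

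**The case against.** The strongest reply is that little is at risk. The ABR itself has no category filter, and it serves the secondary objective on bleeds requiring treatment. FVIII use is summarised by category, so adverse-event FVIII is visible. Section 12.1 keeps non-serious bleeds out of adverse-event reporting, so few infusions should land in that category, and nothing in the SAP says that FVIII for a serious bleed must be recorded there. The SAP also presents the treated-bleed definition as a published standard.

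Most of this stands, and it limits the size of the point. It does not remove the inconsistency. Nor does reporting both rates isolate the problem. The treated-bleed rules also count same-day bleeds separately, merge same-site bleeds within 72 hours of the last treatment, and leave surgical bleeds out of the primary analysis. A gap between the two rates could therefore have several causes.

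A reader might infer more than the SAP supports:

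- **Bleeds disappear from the ABR altogether.** They do not; only the treated-bleed version and the Section 11.2.1 treated-bleed counts are exposed.
- **All traumatic bleeds are removed.** The category is defined by what would occur without haemophilia, which is not the same as traumatic. Section 11.2 also allows ABR summaries by cause, including traumatic.
- **The pre/post comparison is tilted towards BMN 270.** Baseline comes from historical data, and the SAP does not say how those treatments are categorised. One-sided loss is possible but unproven.
- **The Section 11.2.1 regression is biased in a known direction.** If bleeds were lost in the same proportion at all activity levels, the intercept would move and the slope would not. Bias in the slope needs loss that varies with FVIII activity, and nothing shows this.

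**Conclusion.** The point holds in limited form. Followed as written, the SAP can omit an FVIII-treated bleed, possibly a serious one, from the treated-bleed ABR and from the treated-bleed and treated-joint-bleed counts in Section 11.2.1. The cause is a recording category whose boundary two sections draw differently.

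The effect per omitted bleed is fixed by the formula and windows shown above. The total effect cannot be estimated, because the number of affected bleeds is not stated and may be zero. The conclusion assumes that at least some FVIII for bleeds is recorded in the adverse-event category, which the wording of Section 11.2 provides for, and that the bleed does not pair with a later qualifying infusion. No direction of bias relative to baseline, or in the regression slope, is established.

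**What to change.** 1. In Section 11.2, count as treated any bleed on the bleeding eCRF for which FVIII was given, whether the infusion was recorded as treatment for a bleeding episode or for an adverse event. State that serious bleeds are included and that surgery or procedure bleeds remain excluded.
2. State that the same rule applies to the historical pre-infusion period, and how historical treatments are categorised.
3. Reconcile the wording of the adverse-event treatment category with Section 12.1, so that one criterion decides where FVIII for a bleed is recorded.
4. If the narrower definition is kept as the cited standard, say that the exclusion is intended. Add a sensitivity analysis that also counts adverse-event FVIII linked to a bleed record and leaves the other treated-bleed rules unchanged.

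The cost is a few lines of SAP text and one mapping rule linking adverse-event FVIII to bleed records, including data already collected. The treated-bleed ABR may rise slightly.

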11.2.1 Correlation between FVIII Activity and Bleeding Risk

FVIII activity is widely acknowledged to be a key aspect of hemophilia A and a valuable indicator of patients' status, while annualized bleeding rate has been traditionally used as the primary clinical endpoint for replacement therapy. The correlation between FVIII activity level and bleeding risk has been researched, showing that increases in FVIII activity levels are predictably associated with a decreased number of annual bleeds (Den Uijl, 2011, Haemophilia). The following analyses will be performed to explore the relationship between measured FVIII activity and bleeding in this study.

- Based on the FVIII activity visit windows (Appendix 1), median FVIII activity and total number of treated bleeds (defined in Section 11.2) will be calculated for each window for every subject. A negative binomial regression will be performed, modelling number of bleeds in each window vs. FVIII activity in the window. The analysis will be done for FVIII activity measured by one-stage clotting assay and chromogenic assay separately. The same analyses will be conducted for treated joint bleeds. The analysis will use observed cases and be performed for the Full Analysis Set.
- Using a cutoff of FVIII activity level, e.g., 40 IU/dL, each subject's data will be divided into 2 periods: from Week 5 to the first time reaching 40 IU/dL, and from the first time reaching 40 IU/dL to the end of efficacy period. For each period, the duration of the period, the number of bleeds, the ABR, and the change in ABR from baseline will be listed and summarized. The analysis will be performed using various cutoffs, such as 5, 15, 25, 30, 40 IU/dL.

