11.0 EFFICACY EVALUATIONS

This section describes the analyses to be undertaken for the primary, secondary, and other efficacy variables. Efficacy at week 16 after BMN 270 infusion will be analyzed. Long-term efficacy based on data including but not exclusive to week 26, week 52, and up to 5 years post-BMN 270 dosing will be evaluated.

As it is expected to take four weeks for the endogenous production of FVIII following gene transfer to be efficacious, for the purpose of data review and interpretation, the efficacy period will be defined as

Proprietary and Confidential Pg. 15 of 38

starting from week 5 post-BMN 270 dosing until subjects resume routine FVIII prophylaxis, should that occur before the end of the safety long term follow up or ETV, whichever is earlier.

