Week 76	Day 533	Days [519, 546]
Week 80	Day 561	Days [547, 574]
Week 84	Day 589	Days [575, 602]
Week 88	Day 617	Days [603, 630]
Week 92	Day 645	Days [631, 658]
Week 96	Day 673	Days [659, 686]
Week 100	Day 701	Days [687, 714]
Week 104	Day 729	Days [715, 742]
Week 110	Day 771	Days [743, 791]
Week 116	Day 813	Days [792, 833]
Week 122	Day 855	Days [834, 875]
Week 128	Day 897	Days [876, 917]
Week 134	Day 939	Days [918, 959]
Week 140	Day 981	Days [960, 1001]
Week 146	Day 1023	Days [1002, 1043]
Week 152	Day 1065	Days [1044, 1085]
Week 158	Day 1107	Days [1086, 1127]
Week 164	Day 1149	Days [1128, 1169]
Week 170	Day 1191	Days [1170, 1211]
Week 176	Day 1233	Days [1212, 1253]
Week 182	Day 1275	Days [1254, 1295]
Week 188	Day 1317	Days [1296, 1337]
Week 194	Day 1359	Days [1338, 1379]
Week 200	Day 1401	Days [1380, 1421]
Week 206	Day 1443	Days [1422, 1463]
Week 212	Day 1485	Days [1464, 1505]
 Week 218	Day 1527	Days [1506, 1547]

Proprietary and Confidential Pg. 36 of 38

Week 224	Day 1569	Days [1548, 1589]
Week 230	Day 1611	Days [1590, 1631]
Week 236	Day 1653	Days [1632, 1673]
Week 242	Day 1695	Days [1674, 1715]
Week 248	Day 1737	Days [1716, 1757]
Week 254	Day 1779	Days [1758, 1799]
Week 260	Day 1821	Days [1800, 1841]

For early termination visit (ETV), the window of last derived visit before ETV will end at one day before ETV

Proprietary and Confidential Pg. 37 of 38

^a Relative to the infusion day (day 1)

^b Visit day is calculated by (visit date – date of infusion date + 1) if post infusion and (visit date – date of infusion date) if before infusion

^c Baseline visit value is defined as the last available measurement prior to dosing.

^d FVIII activity assay values within 72-hour interval since last FVIII use are excluded prior to windowing derivation.

^e PCR collection to occur until at least 3 consecutive negative results are obtained. Subjects who have not had 3 consecutive negative samples by Week 52 should continue to have PCR testing every 4 weeks (during Year 2) or every 6 weeks (during Years 3-5) until 3 consecutive negative samples are documented (or upon consultation between the Investigator and Medical Monitor).

^f Urine test starts with week 4, 8, 12, 16, the corresponding windows are Days [2, 42], Days [43, 70], Days [71, 98], Days [99, 126], respectively.

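### The regression of bleeds on FVIII activity in SAP 11.2.1 is not limited to the efficacy period, so windows on routine prophylaxis can pull the slope toward zero

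*SAP*

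**What the plan says.** SAP 11.2.1 gives two analyses of how bleeding relates to FVIII activity.

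- **First bullet.** The windows are the FVIII rows in Appendix 1 of the SAP. The bullet says that "median FVIII activity and total number of treated bleeds (defined in Section 11.2) will be calculated for each window for every subject". The two quantities are then related by a negative binomial model, "modelling number of bleeds in each window vs. FVIII activity in the window". On missing data and population: "The analysis will use observed cases and be performed for the Full Analysis Set". No start, stop or covariate is named. The post-baseline FVIII rows run from Week 1-4 (Days 2 to 32) to Week 260 (ending Day 1841).
- **Second bullet.** Each subject's follow-up is split at a FVIII cutoff. It begins at Week 5 and stops at the end of the efficacy period.

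Section 11.0 introduces that period for reviewing and interpreting the data and has it run "starting from week 5 post-BMN 270 dosing until subjects resume routine FVIII prophylaxis", or to the end of follow-up or early termination.

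For the predictor, Appendix 1 footnote d says: "FVIII activity assay values within 72-hour interval since last FVIII use are excluded prior to windowing derivation". Section 11.1 has the same rule. For the outcome, Section 11.2 counts only bleeds followed by a treatment recorded as given for a bleeding episode. Routine prophylaxis is a separate category of FVIII replacement there and enters neither the bleed count nor the model.

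**The concern.** The predictor and the outcome refer to different FVIII. After the 72-hour exclusion, the predictor approximates vector-derived activity. The bleed count covers the whole window, including days when infused factor protected the subject. If subjects who resume routine prophylaxis are mostly low expressers, which is plausible though the SAP does not say so, that cover sits at the low end of the predictor. Low-FVIII windows then show fewer bleeds than the same endogenous level would produce without cover, and the fitted decline of bleeding with FVIII is too shallow.

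This is the SAP's only regression of bleeding on FVIII activity. It is run for two assays and repeated for treated joint bleeds, so all four fits share the problem. The two bullets would also describe different follow-up for the same question, with no reason given.

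**Working it through.** The SAP states no slope, power or precision for this analysis, so there is no figure to reproduce. The check has a textual part and two illustrations on assumed inputs.

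**1. Does Section 11.0 already limit the first bullet?** The definition is general, but Section 11 does not apply it automatically. Section 11.2 analyses Weeks 1-4 as a calculation period of its own. Its last period, Week 5 and beyond, is defined in Appendix 1 only as Day 33 or later, with no stop at prophylaxis. The second bullet invokes the efficacy period by name; the first does not. A programmer following the first bullet would keep every window.

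**2. Which prophylaxis windows enter?** Under observed cases, a window with no FVIII value outside the 72-hour exclusion has no predictor and drops out. One value outside it is enough to admit the bleed count of a whole window, which is 28 to 49 days long after baseline.

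**3. Two-point illustration.** Assumed rates: 15 bleeds/yr at about 2 IU/dL without prophylaxis, 3/yr at that level with it, 0.5/yr at 50 IU/dL. The true ratio is 15/0.5 = 30. If a share f of low-FVIII windows is on prophylaxis, the low-end rate is 3f + 15(1 − f), and the relative log-slope is ln(ratio)/ln(30).

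| f | Low-end rate | Ratio to 0.5 | Relative log-slope |
|---|---|---|---|
| 0.25 | 12 | 24 | 0.93 |
| 0.50 | 9 | 18 | 0.85 |
| 0.75 | 6 | 12 | 0.73 |
| 1.00 | 3 | 6 | 0.53 |

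With 5/yr on prophylaxis, f = 1 gives a ratio of 10 and ln(10)/ln(30) = 0.68. Every ratio stays above 1.

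**4. Simulation on the Appendix 1 windows.** From the SAP: at most 15 subjects, and 52 post-baseline windows of 31, 28, 38, 49 and 42 days (the overlapping Week 23-26 window left out). Assumed:

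- 20 bleeds/yr at zero FVIII, and a true log-rate slope of −0.05 per IU/dL;
- FVIII of 0-5 IU/dL and all subjects on prophylaxis in Week 1-4;
- 0, 2 or 5 subjects resuming prophylaxis halfway, with FVIII of 0-3 IU/dL from then on;
- a bleed rate ratio on prophylaxis of 1.0, 0.3 or 0.1;
- 100% or 30% of prophylaxis windows evaluable.

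The model was a negative binomial GLM without an offset, since the SAP states none, with 60 runs per scenario. Cells give mean slope with all windows / mean slope within the efficacy period, and the first as a share of the second.

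| Windows | Resuming | Rate ratio | 100% evaluable | 30% evaluable |
|---|---|---|---|---|
| 14 (about 1 year) | 0 | 0.3 | −0.040 / −0.051, 78% | −0.048 / −0.052, 92% |
| 14 | 0 | 0.1 | −0.036 / −0.050, 72% | −0.044 / −0.050, 88% |
| 14 | 2 | 0.3 | −0.035 / −0.053, 66% | −0.044 / −0.051, 86% |
| 14 | 2 | 0.1 | −0.029 / −0.051, 57% | −0.042 / −0.053, 79% |
| 14 | 5 | 0.3 | −0.028 / −0.050, 56% | −0.039 / −0.052, 75% |
| 14 | 5 | 0.1 | −0.020 / −0.048, 42% | −0.035 / −0.053, 66% |
| 52 (5 years) | 0 | 0.3 | −0.052 / −0.055, 95% | −0.053 / −0.054, 98% |
| 52 | 0 | 0.1 | −0.051 / −0.055, 93% | −0.054 / −0.055, 98% |
| 52 | 2 | 0.3 | −0.043 / −0.054, 80% | −0.050 / −0.054, 93% |
| 52 | 2 | 0.1 | −0.040 / −0.055, 73% | −0.050 / −0.056, 89% |
| 52 | 5 | 0.3 | −0.036 / −0.056, 64% | −0.046 / −0.055, 84% |
| 52 | 5 | 0.1 | −0.028 / −0.054, 52% | −0.042 / −0.054, 78% |

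The rows with nobody resuming isolate Week 1-4. With a rate ratio of 1.0 the two fits differed by at most 0.002, so the gap comes from the prophylaxis effect. Restricted slopes ran from −0.048 to −0.056 in all scenarios. The slightly steep five-year values also occur without any prophylaxis effect; longer late windows and no offset are a likely cause. The mean slope was negative everywhere; a positive slope occurred in 1 of 60 runs in one scenario.

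**The case against.** The strongest reply is that Section 11.0 stands at the head of the efficacy section and may be meant to govern all of it, so that only a cross-reference is missing. That is a possible intention, but Section 11.2 and Appendix 1 do not follow it, and the first bullet does not state it.

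Second, the 72-hour rule with observed cases already removes some prophylaxis windows. This stands, and it reduces the bias. How many go is unknown, because the SAP gives no infusion interval. It is also not known that anyone will resume: Section 11.0 treats resumption as conditional.

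Third, a reader might infer more than the documents support:

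- **That low FVIII would look protective.** It would not. Low FVIII still bleeds more in every illustration above; the slope is shallower, not reversed.
- **That Week 1-4 is a large part of the problem.** The SAP does not say that subjects are on prophylaxis then, and on-demand subjects are eligible. Even if all were, the five-year slope hardly moves.
- **That the 5 IU/dL target is undermined.** That threshold is set in the objectives and the primary endpoint and is not derived from this model.

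Fourth, the remedy has limits. Cutting a window at resumption shortens exposure, so without an offset it would show fewer bleeds mechanically. Stopping at resumption may be informative if subjects resume because of low FVIII or bleeding. Precautionary and surgical FVIII cover would remain. These points stand and shape the fix.

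**Conclusion.** The concern holds as attenuation. As written, the first bullet of 11.2.1 admits windows outside the efficacy period and has no term for exogenous FVIII, so the inverse FVIII-bleeding slope is biased toward zero wherever prophylaxis windows have evaluable values and prophylaxis lowers bleeding. Resumed prophylaxis is the main driver. Week 1-4 matters mostly in analyses of about one year, and only if subjects are on prophylaxis then.

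The size cannot be fixed from the SAP, which gives neither the number resuming nor the share of their windows that is evaluable. Over the assumed range it runs from almost nothing (98% of the restricted slope retained) to a loss of more than half (42% retained). All rates, slopes and resumption patterns behind those figures are assumptions. The analysis is exploratory, in at most 15 subjects, and the primary endpoint is unaffected. The change is worth making because it is cheap and brings the two bullets onto the same follow-up.

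**What to change.** In the first bullet of 11.2.1, limit the regression to windows within the Section 11.0 efficacy period, from Week 5-8 until routine prophylaxis resumes. For a window cut short at resumption, either include log(days at risk) as an offset and count only FVIII values and bleeds before resumption, or drop the window whole; state which. As a sensitivity analysis, fit all post-infusion windows with a yes/no term for routine prophylaxis in the window.

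The cost is a few lines of SAP text and a filter on a FVIII-use category that is already summarised. The restriction leaves fewer low-FVIII windows, so the interval is wider at that end. The offset was not part of the simulation, in which resumption always fell on a window boundary. The report should say that stopping at resumption may be informative and that precautionary and surgical FVIII cover is not removed.
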